4.4.1.3 Supportive Analyses

A PP analysis will be performed on the Change in mean organoleptic score from Baseline (pre-brushing) to 3 weeks (pre-brushing) if there is more than 10% difference in the number of subjects between the PP and mITT populations. A decision on whether a PP analysis will be performed will be made prior to study unblinding (release of the randomization codes).

A summary of the mean breath organoleptic score endpoints will be presented for the PP Population in Table 14.2.2.1.2. Statistical analysis of mean breath organoleptic score will be presented for the PP population in Table 14.2.2.2.2. In addition, the mean breath organoleptic score (Figure 14.2.1.2) at each time point will be plotted by study product for all subjects in PP Population.

4.4.2 Secondary Efficacy Variables

All secondary endpoint analyses will be performed on the mITT population. There will be no adjustment for multiplicity in the analyses described in this section.

Secondary efficacy endpoints are:

- Mean total VSC concentration in breath.
- Mean hydrogen sulfide, methanethiol and dimethyl sulfide concentration in breath.
- Mean breath organoleptic scores.

Secondary efficacy variables are defined as:

- Change from baseline (pre-brushing) to 3 weeks (pre-brushing) in mean total VSC concentration in breath.

- Change from baseline (pre-brushing) to 3 weeks (pre-brushing) in mean hydrogen sulfide, methanethiol and dimethyl sulfide concentration in breath.
- Change from baseline (pre-brushing) to 3 weeks (1 hour post-brushing) in mean total VSC concentration in breath.
- Change from baseline (pre-brushing) to 3 weeks (1 hour post-brushing) in mean hydrogen sulfide, methanethiol and dimethyl sulfide concentration in breath.
- Change from baseline (pre-brushing) to 3 weeks (1 hour post-brushing) in mean breath organoleptic scores.
- Change from pre-brushing to 1 hour post brushing at Baseline and after 3 weeks in mean total VSC concentration in breath.
- Change from pre-brushing to 1 hour post brushing at Baseline and after 3 weeks in mean hydrogen sulfide, methanethiol and dimethyl sulfide concentration in breath.
- Change from pre-brushing to 1 hour post brushing at Baseline and after 3 weeks in mean breath organoleptic scores.

4.4.2.1 Secondary Efficacy Variable 1

Mouth air VSC determination will be performed pre- and 1 hour (± 5 minutes) post-brushing at Visits 2&3. The mouth air sample will be evaluated using the OralChroma Halitosis Measuring instrument (Model CHM-2 [Nissha FIS, Inc.; Osaka, Japan]) in agreement with the manufacturer's instructions. The OralChroma is a portable gas chromatograph with a highly sensitive semiconductor gas detector which can determine the concentration of the 3 main VSCs in breath (hydrogen sulfide, methane thiol and dimethyl sulfide).

There will be individual evaluations of hydrogen sulfide, methanethiol and dimethyl sulfide concentrations in breath taken at each visit (Baseline and Week 3) at each time point (pre-brushing /1-hour post-brushing).

The Total VSC at a visit/time point will have two samples and will be derived as the sum of the hydrogen sulfide, methanethiol and dimethyl sulfide concentrations in breath and then the mean over two samples to derive one value used for analysis per visit/timewpoint. The sum and the average will be performed on the raw scale and final value will be transformed.

For each concentration (hydrogen sulfide, methanethiol, dimethyl sulfide, Total VSC), there will be two samples and will be considered as average of two samples before the result are log (base 10) transformed for analysis purpose.

The raw and logged concentration descriptive statistics (n, mean, SD, SE, Geometric mean, Geometric SD, Geometric coefficient of variation(CV), median, minimum, and maximum) will be presented for change from baseline (for each type of baseline detailed below) in each concentration (hydrogen sulfide, methanethiol, dimethyl sulfide, Total VSC) at each assessment time point in, respectively, (Table 14.2.3.1.1, Table 14.2.3.1.2, Table 14.2.3.1.3, Table 14.2.3.1.4 respectively). for all subjects in mITT Population by study product. Raw means (\pm

SE) of each concentration (hydrogen sulfide, methanethiol, dimethyl sulfide, Total VSC) at each time point will be plotted by study product respectively in Figure 14.2.2.1 for all subjects in mITT population.

Individual concentration data for each concentration parameter (hydrogen sulfide, methanethiol, dimethyl sulfide, Total VSC) will be listed for each subject by visit and study product group in Listing 16.2.6.2 for all randomized subjects.

4.4.2.1.1 Statistical Hypothesis, Model and Method of Analysis

Study product differences will be tested under the null hypothesis:

- H_0 : There is no treatment difference
- H_1 : There is a treatment difference

The following study product comparisons will be analyzed:

- Experimental Dentifrice versus Reference Dentifrice

The ANCOVA models described below will be applied for each of the mean concentrations using a different definition of Baseline and post-baseline as follows:

- Baseline = Baseline (pre-brushing), Post-baseline = Week 3 (pre-brushing)
- Baseline = Baseline (pre-brushing), Post-baseline = Week 3 (1-hour post-brushing)
- Baseline = Baseline (pre-brushing), Post-baseline = Baseline (1-hour post-brushing)
- Baseline = Week 3 (pre-brushing), Post-baseline = Week 3 (1-hour post-brushing)

All concentration values will be log (base 10) transformed including baseline for each parameter. The corresponding change from baseline in the logged value will be analyzed for each postbaseline concentration (hydrogen sulfide, methanethiol, dimethyl sulfide, Total VSC) using an ANCOVA model with study product and gender as fixed effects and the respective logged mean Baseline concentration as a covariate. The least square means for each study product will be based on observed margins to test for < 0 change (on the logged scale) from baseline. The difference between least square means for the Experimental Dentifrice compared to the Reference Dentifrice will be used to test for a difference between products. As well as presenting the least square means and differences on the log scale, the corresponding back transformed values (antilog base 10) will be presented to represent percent reduction from baseline and percent difference from control relative to baseline. The two-sided p-values and 95% CIs (logged and back-transformed) will be provided.

Using the above model for each of the definition mentioned above, adjusted mean change [log (base 10)-based] from each baseline and percent reduction (back-transformed) from each baseline, along with corresponding 95% CIs will be reported by study product group will be provided for each concentration parameters (hydrogen sulfide, methanethiol, dimethyl sulfide, Total VSC) respectively in Table 14.2.3.2.1, Table 14.2.3.2.2, Table 14.2.3.2.3, Table 14.2.3.2.4 (with baseline as Day 0 pre-brushing) and respectively in Table 14.2.3.3.1, Table 14.2.3.3.2, Table 14.2.3.3.3, Table 14.2.3.3.4 (with baseline as Week 3 pre-brushing). Also, p-

values testing for negative change from baseline will be presented for study product groups. Mean difference between study product groups [Log (base 10) based], percent difference (back-transformed) from control relative to each baseline, corresponding 95% CIs and p-values will be provided for each concentration parameters (hydrogen sulfide, methanethiol, dimethyl sulfide, Total VSC) respectively in Table 14.2.3.2.1, Table 14.2.3.2.2, Table 14.2.3.2.3, Table 14.2.3.2.4 (with baseline as Day 0 pre-brushing) and respectively in Table 14.2.3.3.1, Table 14.2.3.3.2, Table 14.2.3.3.3, Table 14.2.3.3.4 (with baseline as Week 3 pre-brushing). This will be assessed at the two-sided 5% significance level.

The assumption of normality and homogeneity of variance in the above described ANCOVA analyses will not be investigated, because the analysis will be performed on log (base 10) transformed data.

4.4.2.2 Secondary Efficacy Variable 2

Secondary endpoint is the change in mean breath organoleptic score:

At following Baseline and post-baseline definitions:

- Baseline = Baseline (pre-brushing), Post-baseline = Week 3 (1-hour post-brushing)
- Baseline = Baseline (pre-brushing), Post-baseline = Baseline (1-hour post-brushing)
- Baseline = Week 3 (pre-brushing), Post-baseline = Week 3 (1-hour post-brushing)

Descriptive statistics (n, mean, SD, SE, median, minimum, and maximum) will be presented for mean breath organoleptic score at each assessment time point in Table 14.2.2.1.1 for all subjects in mITT population by study product. Raw means (\pm SE) of the mean breath organoleptic score at each time point will be plotted by study product in Figure 14.2.1.1 for all subjects in mITT population.

Individual breath organoleptic score data will be listed for each subject by visit and study product group in Listing 16.2.6.1 for all randomized subjects.

4.4.2.2.1 Statistical Hypothesis, Model and Method of Analysis

Study product differences will be tested under the null hypothesis:

- H_0 : There is no treatment difference
- H_1 : There is a treatment difference

The following study product comparisons will be analyzed:

- Experimental Dentifrice versus Reference Dentifrice

A similar ANCOVA model as used for the primary analysis (as described in [Section 4.4.1.2](#)) will be used but with the appropriate pre-brushing and post-baseline result used accordingly.

Using the above model for each of the definition mentioned above, adjusted mean change from each baseline, along with 95% CIs will be reported by study product group will be provided for mean breath organoleptic score in Table 14.2.4.1 (with baseline as Day 0 pre-brushing) and

Table 14.2.4.2 (with baseline as Week 3 pre-brushing). Also, p-values testing for negative change from baseline will be presented for study product groups. Mean difference between study product groups, 95% CIs and p-values will be provided for mean breath organoleptic score in Table 14.2.4.1 (with baseline as Day 0 pre-brushing) and Table 14.2.4.2 (with baseline as Week 3 pre-brushing). This will be assessed at the two-sided 5% significance level.

The assumption of normality and homogeneity of variance in the ANCOVA will be investigated. In case of violation of these assumptions, a suitable nonparametric test (the Van Elteren test, adjusted for gender) will be performed, and results will be provided to support the ANCOVA results. If the inferences from the two analyses are similar, then both sets of results will be reported and emphasis will be made on the ANCOVA results. In case of discrepancies between inferences of the ANCOVA and non-parametric analysis, results will be drawn from the non-parametric analysis.

4.4.3 Handling of Missing Values/Censoring/Discontinuations

All missing data for primary and secondary endpoints will be treated as missing data and not imputed. In the event that one of the hydrogen sulfide, methanethiol or dimethyl sulfide concentrations are missing then the Total VSC will also be treated as missing.

For analysis of VSC, if there is case when any individual concentration value is 0, it will be imputed as 0.01 for log (base 10) transformed analysis. For summary of raw data, 0 values will be considered as is.

4.5 Analysis of Safety

The safety profile of the study treatments will be assessed with respect to AEs, incidents and OST/OHT abnormalities in oral health study.

4.5.1 Adverse Events and Serious Adverse Events

All AEs will be reviewed by the Clinical Research Scientist or Designee prior to database lock, prior to unblinding and will be coded to a system organ class (SOC) and preferred term (PT) using the Medical Dictionary for Regulatory Activities (MedDRA).

AEs will be classified as oral and non-oral on the AE page of eCRF.

Treatment emergent adverse events (TEAEs) are defined as new AEs that occur on or after the first study product use (if this date is missing a suitable alternative will be used e.g., date of randomization). Adverse events with an onset date/time prior to the first study product use will be considered as non-treatment emergent.

The following summary tables and listings will be presented by study product group.

- Table of TEAEs by SOC and PT (Table 14.3.1.1).
- Table of TEAEs by Oral/Non-Oral and PT (Table 14.3.1.2)
- Table of treatment related TEAEs by SOC and PT (Table 14.3.1.3)

- Table of treatment related TEAEs by Oral/Non-Oral and PT (Table 14.3.1.4)
- Table of AEs related to COVID-19 by SOC and PT (Table 14.3.1.5).
- Listing of all AEs (Listing 16.2.7.1 for all randomized subjects; Listing 16.2.7.2 for non-randomized subjects)
- Listing of deaths (Listing 14.3.2.1)
- Listing of non-fatal SAEs (Listing 14.3.2.2)
- Listing of TEAEs leading to study or drug withdrawal (Listing 14.3.2.3)
- Listing of TEAEs classified as Oral (Listing 14.3.2.4)
- Listing of all AEs related to COVID-19 (Listing 16.2.7.3 for all screened subjects)

In the event that there is nothing to report, a null table or listing will be produced. All Incidents will be listed in Listing 16.2.7.4. In the event that there is nothing to report, a null listing will be produced.

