8.1.1.8 Subject Eligibility

The investigator and/or medically qualified designee will review the inclusion/exclusion criteria, medical history, prior and current medications/treatments and the findings of the oral examinations to confirm subject eligibility to participate in the clinical trial. This will be documented in the CRF.

Eligible subjects will be appointed to attend the study site for baseline assessments (Visit 2) a minimum of 7 days, and a maximum of 21 days, after their screening visit and will be instructed to use only their supplied oral care products [washout products] (according to their normal habit) until their next appointment.

To prepare for study participation, subjects will be instructed in the [Lifestyle Guidelines](#) and any [Concomitant Medication/Treatment\(s\)](#) requirements of the protocol.

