10.1 Definition of an Adverse Event (AE)

An AE is any untoward medical occurrence in a clinical study subject, temporally associated with the use of a study product including any washout or lead-in product (or medical device), whether or not considered related to the study product, including any washout or lead-in product (or medical device).

NOTE: An AE can therefore be any unfavorable and unintended sign (including an abnormal laboratory finding), symptom, or disease (new or exacerbated) temporally associated with the use of a study product including any washout or lead-in product (or medical device).

Events Meeting the AE Definition:

- Any abnormal laboratory test results (hematology, clinical chemistry, or urinalysis) or other safety assessments (e.g. ECG, radiological scans, vital sign measurements), including those that worsen from baseline, considered clinically significant in the medical and scientific judgment of the investigator (i.e., not related to progression of underlying disease).
- Exacerbation of a chronic or intermittent pre-existing condition including either an increase in frequency and/or intensity of the condition.
- New conditions detected or diagnosed after study product administration even though it may have been present before the start of the study.
- Signs, symptoms, or the clinical sequelae of a suspected drug-drug interaction.
- Signs, symptoms, or the clinical sequelae of a suspected overdose of either study product or a concomitant medication. Overdose per se will not be reported as an AE/SAE unless it is an intentional overdose taken with possible suicidal/self-harming intent. Such overdoses should be reported regardless of sequelae.
- "Lack of efficacy" or "failure of expected pharmacological action" per se will not be reported as an AE. Such instances will be captured in the efficacy assessments. However, the signs, symptoms, and/or clinical sequelae resulting from lack of efficacy will be reported as AE if they fulfill the definition of an AE.

Events NOT meeting the AE definition:

- Any clinically significant abnormal laboratory findings (if applicable) or other abnormal safety assessments which are associated with the underlying disease, unless judged by the investigator to be more severe than expected for the subject's condition.
- The disease/disorder being studied or expected progression, signs, or symptoms of the disease/disorder being studied, unless more severe than expected for the subject's condition.

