10.3 Time Period and Frequency for Collecting AE and SAE Information

All AEs, and therefore all SAEs will be collected immediately after a subject provides consent to participate in the study by the completion (signature) of the ICF and until 5 days following last administration of the study product (or last procedure).

Medical occurrences that began before obtaining informed consent will be recorded in the Medical History/Current Medical Conditions section of the CRF not the AE section.

Details recorded by the subject on a diary or similar document that meet the definition of an AE must also be discussed with the subjects and transcribed in the AE section of the CRF.

All SAEs will be recorded and reported to the sponsor or designee immediately and under no circumstance should this exceed 24 hours. The investigator will submit any updated SAE data to the sponsor within 24 hours of it being available.

Investigators are not obligated to actively seek AEs or SAEs after the conclusion of the study participation. However, if the investigator learns of any SAE, including a death, at any time after a subject has been discharged from the study, and they consider the event to be reasonably related to the study product or study participation, the investigator must promptly notify the sponsor.

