10.6 Follow-up of AEs and SAEs

After the initial AE/SAE report, the investigator is required to proactively follow up with each subject and provide further information on the subject's condition.

All AEs (serious and non-serious) will be followed until resolution, until the condition stabilizes, until the event is otherwise explained, or until the subject is lost to follow-up.

The investigator is obligated to perform or arrange for the conduct of supplemental measurements and/or evaluations as may be indicated or as requested by the sponsor to elucidate as fully as possible the nature and/or causality of the AE. This may include additional laboratory tests or investigations, histopathological examinations, or consultation with other health care professionals.

New or updated information will be recorded on the AE CRF page and on the SAE form (subject to the classification of the AE).

The investigator will submit any updated SAE data to the sponsor within 24 hours of receipt of the information.

Investigators are not obliged to actively seek AEs in former subjects. However, if the investigator learns of a SAE, including death, at any time after a subject has been discharged from the study, and considers the event reasonably related to the study product or study participation, the investigator will promptly notify the sponsor by emailing the information to the Case Management Group mailbox at (PPD [REDACTED]), with copy to the appropriate CH Study Manager.

The investigator will submit any updated SAE data to the sponsor within the designated reporting time frames.

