12.3.3 Safety Analysis

The Safety population will be used for safety analyses. Safety analyses will be performed according to study product received.

Safety analyses will focus on:

- Adverse Events (AEs)

All AEs will be reviewed by the Clinical Research Scientist, or designee, prior to database lock and unblinding and will be coded using the MedDRA. AEs will be categorized as oral and non-oral by the examiner prior to database lock. AEs will be regarded as 'treatment' emergent if they occur on or after the first use of study product at the Baseline visit.

The following AEs summaries (number of distinct AEs and frequency/proportion of subjects affected will be presented by study product group and overall:

- Treatment emergent AEs
- Treatment emergent AEs by System Organ Class (SOC) and Preferred Term (PT);
- Treatment emergent AEs by Oral/Non-Oral and PT;
- Treatment emergent treatment related AEs by Oral/Non-Oral and PT;
- Treatment emergent treatment related serious AEs by SOC and PT;

A listing of all AEs will be presented for all subjects in the Safety population. Separate listings will be presented for any deaths, serious AEs and AEs leading to study or product discontinuation.

- Oral Soft Tissue and Examinations
 - Summary of abnormalities at each visit for each area examined
- Oral Hard Tissue and Examinations
 - Will be listed only.
- Exposure and compliance with study product
 - Detailed in section 12.3.6.1.

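### The treatment-emergent rule does not cover adverse events that start in washout and worsen on the study dentifrice, and neither document says how such worsening is recorded

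*SAP*

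**What the plan says.** SAP 4.5.1 contains two sentences on the matter. The first is the definition: "Treatment emergent adverse events (TEAEs) are defined as new AEs that occur on or after the first study product use". The second handles the remainder: "Adverse events with an onset date/time prior to the first study product use will be considered as non-treatment emergent". Neither mentions an event that starts earlier and then worsens. Protocol 12.3.3 also uses a date rule without a worsening clause: "AEs will be regarded as 'treatment' emergent if they occur on or after the first use of study product at the Baseline visit".

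Collection begins well before first use. Under protocol 10.3, "All AEs, and therefore all SAEs will be collected immediately after a subject provides consent to participate in the study". Under protocol 8.1.1.8, Visit 2 takes place "a minimum of 7 days, and a maximum of 21 days, after their screening visit", and subjects use the washout dentifrice in between.

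Protocol 10.1 includes worsening in its concept of an adverse event. It covers any sign, "symptom, or disease (new or exacerbated) temporally associated with the use of a study product including any washout or lead-in product", and lists as an example: "Exacerbation of a chronic or intermittent pre-existing condition including either an increase in frequency and/or intensity of the condition". Protocol 9.3.1 and SAP 4.5.2.1 likewise make worsening of an existing oral soft tissue (OST) condition after screening a recordable adverse event.

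On follow-up of an event already reported, protocol 10.6 says: "New or updated information will be recorded on the AE CRF page and on the SAE form", with use of the SAE form depending on how the event is classified.

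**The concern.** The protocol regards exacerbation as an adverse event, but the SAP's TEAE rule looks only at when an event started. Suppose a mild oral ulcer or gingival irritation begins during washout and becomes moderate or severe once the study dentifrice is in use. That worsening is an on-product tolerability finding. Under SAP 4.5.1, whether it counts depends on how the site happened to record it.

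The stakes are limited but real. TEAEs are the only safety endpoint in the objectives tables of both documents. Protocol 2.3 says the exact experimental formulation has not been clinically tested before. An event lost from the TEAE tables is lost from the only adverse event summaries that compare the arms, apart from the COVID-19 table.

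**Working it through.** No arithmetic settles this. The check is to follow one event through the rules: a mild oral event with onset in washout that becomes moderate after first study product use.

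1. **Is it captured?** Yes. Onset is after consent, so protocol 10.3 puts it in the adverse event section of the CRF, with a washout onset date.
2. **Is the worsening reportable?** Yes in substance, under protocol 10.1 and, for soft tissue, 9.3.1. Both passages refer to a pre-existing condition, and neither says whether that includes an event that arose in washout.
3. **How is the worsening recorded?** Not stated. Protocol 10.6 sends updates to the adverse event page without saying whether a rise in intensity opens a second record. Protocol 10.5.1 asks for one intensity category per event and does not say what happens when intensity changes.
4. **How is it classified?**
   - *Recorded as an update.* The onset stays in washout and SAP 4.5.1 makes the event non-treatment emergent. It is absent from Tables 14.3.1.1 to 14.3.1.4 and from Listings 14.3.2.3 (TEAEs leading to discontinuation) and 14.3.2.4 (oral TEAEs). This holds even if it is judged related or causes withdrawal.
   - *Recorded as a separate event.* The onset is after first use and meets the date rule in both documents. The word *new* in the SAP definition leaves some doubt about whether it qualifies.
5. **Where is it visible in either case?** Listing 16.2.7.1 shows all adverse events of randomized subjects. Listings 14.3.2.1 and 14.3.2.2 show deaths and non-fatal serious events without a TEAE restriction. Table 14.3.4.1 gives the OST results.

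A related mismatch appears in the listings. Protocol 12.3.3 promises a listing of adverse events that led to stopping the study or the product, with no TEAE restriction. SAP 4.5.1 and Appendix 1 restrict Listing 14.3.2.3 to TEAEs. On the update route, a washout-onset event that worsens and causes withdrawal belongs in the protocol's listing but not in the SAP's. SAP section 5 nevertheless reports no changes from the protocol.

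For scale only: with about 53 subjects per arm, one subject whose sole on-product event is missed changes that arm's TEAE proportion by 1/53 = 1.9 percentage points.

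**The case against.** The strongest reply is that nothing need be lost. Protocol 10.6 names the type of form, not the existing record. Where the protocol means the original form it says so, as protocol 10.12 does for device incidents. Protocol 10.1 and 9.3.1 make worsening an adverse event in its own right, so a site could properly enter it with an on-treatment onset. This stands, and it makes the loss conditional. A reader might infer from SAP 4.5.1 that every washout event that worsens drops out of all the TEAE tables. The documents do not support that, because they leave the recording route open.

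Second, the affected group is narrow. Conditions that began before consent, including the gingivitis required for entry, go into medical history under protocol 10.3. If they worsen on product enough to count as an adverse event, the onset is on treatment. Eligibility is also reviewed at Visit 2 before randomization, and inclusion criterion 5b excludes lesions that could interfere with evaluations. This largely stands. However, protocol 8.2.1 places the Visit 2 OST examination after randomization and first brushing, so an unreported mild lesion can pass into treatment.

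Third, the event remains visible elsewhere. Withdrawals are also tabulated by reason and study product in Table 14.1.1. This stands in part. OST findings are recorded only as normal or abnormal with descriptive detail, so a lesion that is mild at Visit 2 and worse at Visit 3 can count as abnormal at both. Line listings do not enter the summarized comparison between arms.

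**Conclusion.** The gap is real and minor. The SAP states an explicit exclusion for earlier-onset events, has no worsening provision, and leaves the outcome to an unwritten recording convention. If worsening is kept as an update, it is missing from the four TEAE tables and two TEAE listings. If it is entered separately, it probably reaches them. The narrowing of Listing 14.3.2.3 does not depend on that convention.

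The number of affected events cannot be derived from the documents. A reader might try to size the problem from visit timing. With 7 to 21 days of washout, 21 to 23 days of treatment and an assumed constant onset rate, 7/(7+23) = 23% to 21/(21+21) = 50% of events starting between screening and Visit 3 would begin before treatment. That figure should not be used as the size of the problem. It counts all pre-treatment onsets, including events that resolve or stay unchanged and are rightly non-emergent. The documents give no figure for the share that worsens on product.

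Safety is summarized descriptively, no decision rule depends on it, and no efficacy analysis is affected.

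**What to change.** - In SAP 4.5.1 and protocol 12.3.3, define a TEAE as an adverse event with onset on or after first study product use, or with earlier onset that increases in intensity or becomes serious on or after first use.
- Qualify the SAP sentence on earlier-onset events so that it covers only those that do not worsen in this way.
- Add a CRF completion instruction that such worsening is entered as a separate adverse event dated at the worsening. The washout record then keeps its own onset and intensity, and the worsening is counted once.
- Restore Listing 14.3.2.3 to all adverse events leading to study or product discontinuation, as protocol 12.3.3 provides.

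The cost is a few lines of text and one site instruction, with no added assessments. The reported TEAE rate may rise slightly.
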